Appendix 20.2.4 shows example SAS code for generating descriptive statistics.

10.7 Exploratory Efficacy Endpoints and Analyses

Ocular discomfort associated with conjunctivitis symptoms will be assessed through the Ocular Discomfort Scale. The Ocular Discomfort Scale is composed of three items: eye pain, itching, and foreign body sensation. The subject will be asked three questions about his/her experience with pink eye over the past 24 hours: how bad was your eye pain (for example, a hurting, burning, or stinging feeling in your eye) at its worst; how bad was the feeling that something was in your eye (like an eyelash or dirt) from your pink eye at its worst; how bad was the itching from your pink eye at its worst. All questions will be evaluated using a 0-10 scale with 0 indicating no symptom and higher score indicating more severe symptom. A separate scale will be administered for children less than 8 years of age, which has a single question for the parent about whether his/her child experienced eye pain or discomfort because of pink eye over the past 24 hours (child rubbing his/her eyes, crying or tearing up, and/or telling parent that he/she is having pain or discomfort) with a Yes/No answer.

The ocular discomfort endpoints will be collected at Visit 2 (Day 3), Visit 3 (Day 5), Visit 4 (Day 8), and Visit 5 (Day 12). For the ocular discomfort endpoints obtained from the scale for adults and children 8 years and older (individual scores and total score), absolute and change from baseline of ocular discomfort scores due to conjunctivitis symptoms will be summarized by treatment group at each visit in mITT and ITT population.

The binary ocular discomfort endpoint obtained from children less than 8 years of age will also be summarized by treatment group at each visit in mITT and ITT population.

No hypothesis testing will be conducted for the exploratory efficacy endpoints. Similar to secondary efficacy endpoints, all exploratory efficacy endpoints will be summarized by treatment group using descriptive statistics at each assessment visit. Continuous endpoints will be summarized by number of subjects (n), mean, median, SD, minimum, maximum and two-sided 95% CI. Binary endpoints will be summarized by number of subjects (n), frequency, proportion and two-sided 95% CI (exact CI for binominal proportion).

11. SAFETY ANALYSES

The safety analysis will be performed using the Safety Population. Safety variables include adverse events (AEs; including local tolerability), slit lamp biomicroscopy, non-dilated/dilated fundus exam, red reflex exam, best corrected visual acuity (BCVA), and urine pregnancy testing (for females of childbearing potential) variables.

Safety data collected at baseline (Visit 1) will be used as the baseline value for safety analysis.

All safety analyses will be conducted according to the treatment the subject actually received.

11.1 Adverse Events

AEs will be coded using MedDRA version 19.1. Any AE that occurs after the first dose of investigational product instillation will be considered a treatment-emergent adverse event (TEAE).

An overall summary of the number of subjects with TEAEs will be presented, including the number and percentage of subjects with any TEAEs, ocular TEAEs, non-ocular TEAEs, TEAEs leading to death, serious TEAEs, TEAEs related to investigational product and TEAEs leading to discontinuation of investigational product as well as the total number of events in each category.

The number and percentage of subjects reporting TEAEs in each treatment group and across all subjects will be tabulated by SOC and preferred term as well as by SOC, preferred term, and maximum severity. TEAEs considered related to investigational product will also be summarized by SOC and preferred term. If more than 1 AE occurs with the same SOC/preferred term for the same subject, then the subject will be counted only once for that SOC/preferred term using the most severe and most related occurrence for the summarization by severity and by relationship to investigational product, respectively. The incidence of common TEAEs ($\geq 5\%$ of subjects in any treatment group) will also be summarized by SOC and preferred term. Serious TEAEs, TEAEs leading to discontinuation of investigational product and TEAEs leading to death, will be summarized by SOC, preferred term and treatment group and across all subjects. The number and percentage of subjects reporting local tolerability TEAEs in each treatment group and across all subjects will also be tabulated. Local tolerability TEAEs (overall, related to IP and not related to IP) will be tabulated by SOC and preferred term. Preferred terms that are considered to be local tolerability AEs will be provided by global drug safety (GDS) before database lock. Separate tables will be generated for ocular TEAEs and non-ocular TEAEs. For all above tables, ocular TEAEs will be summarized at subject level and also by study eye, fellow eye and both eyes.

Listings of all TEAEs will be provided by subject.

Pre-treatment events (captured on the AE form that occurred prior to the first dose of investigational product) will be listed by subject but not tabulated.

Imputed dates, severity and relationship to investigational product (see Section 18.7, 18.8 and 18.9 respectively for imputation rules) will be marked in the listings.

11.2 Other Safety Variables

The following safety measures will be descriptively summarized by study eye and fellow eye and by treatment group and across all subjects at each visit:

- Best corrected visual acuity (BCVA, logMAR scoring) and change from baseline BCVA
- Slit lamp biomicroscopy (normal, abnormal – not clinically significant, abnormal – clinically significant) for 6 anatomic anterior segment regions: lids, conjunctiva, cornea, iris, anterior chamber and lens
- Non-dilated/ Dilated Fundus examination (normal, abnormal – not clinically significant, abnormal – clinically significant) for 3 anatomic posterior segment regions: vitreous, optic nerve and macula
- Red reflex examination (normal, abnormal– not clinically significant, abnormal – clinically significant) for infants and small children in whom a fundus examination cannot be done

Continuous endpoints will be summarized by number of subjects (n), mean, median, SD, SE, minimum and maximum. Binary endpoints will be summarized by number of subjects (n), frequency and percentage.

BCVA/change from baseline BCVA and slit lamp biomicroscopy at each visit as well as non-dilated/ dilated fundus examination (or red reflex exam for infants and small children in whom a fundus examination cannot be done), and pregnancy test results at visits 1 and 5/early termination will be provided by subject in Safety Population in data listings. A by subject listing will also be generated for chlamydia and gonorrhea results at Visit 1 in Safety Population in subjects less than 2 month of age and for Herpes Simplex Virus (HSV) at Visit 1 in Safety Population.

12. CLINICAL PHARMACOKINETIC AND PHARMACODYNAMIC ANALYSES

Not applicable.

13. OTHER ANALYSES

Subgroup analyses will be performed on the primary and key secondary efficacy endpoint. The following subgroups will be used: age stratum (< 6 years, 6 to <18 years, \geq 18 years and overall pediatric group, i.e. <18 years), gender, race, ethnicity, iris color of the study eye and region. The planned regions and countries are: North America (Canada and United States including Puerto Rico), South America (Colombia, Peru), Asia-Pacific (Australia, India and Philippines), Europe (Austria, Estonia, France, Germany, Hungary, Italy, Poland, Spain and United Kingdom) and Middle East/Africa (Israel, South Africa). Descriptive statistics (number of subjects [n], frequency, proportion, two-sided 95% exact CI for binominal proportion) will be generated for the primary and key secondary efficacy endpoints by treatment group in mITT. Pairwise difference in response rates and corresponding two-sided 95% asymptotic CI for the difference will also be generated in mITT. No hypothesis testing will be conducted as the study is not powered to detect treatment effect within subgroups.

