2.5 Determination of Sample Size

The sample size was estimated for the primary comparison of SHP640 versus placebo on clinical resolution in the treatment of subjects with bacterial conjunctivitis in the study eye at Visit 3 (Day 5) using nQuery Advisor 7.0. Subjects will be randomized 3:1:3 to receive either SHP640, PVP-I, or placebo within each age stratum.

The primary efficacy endpoint is clinical resolution status (defined as absence [ie, a score of 0] of bulbar conjunctival injection and ocular conjunctival discharge) in the study eye at Visit 3 (Day 5) between SHP640 and placebo. The null hypothesis to be tested is that there is no difference in proportion of subjects with clinical resolution in the study eye between SHP640 ophthalmic suspension and placebo with the alternative of the non-zero difference in the proportion with clinical resolution between them.

A sample size of 504 subjects (216 subjects in each of the SHP640 and placebo groups, 72 in PVP-I group) will ensure ~90% power to compare the SHP640 and placebo treatment groups assuming 61% and 45% subjects with clinical resolution, respectively, using Fisher's Exact test at 2-sided 5% level of significance.

All efficacy analyses will be based on the modified Intent-to-Treat (mITT) population (refer to Section 4.4 for the definition of mITT) with post-baseline last observation carried forward (LOCF) for the subjects with missing clinical resolution status at Visit 3 (Day 5). To ensure 504 subjects in the mITT population, approximately 721 subjects will be randomized in this study (approximately 309 subjects in each of SHP640 and placebo groups; approximately 103 subjects in PVP-I group).

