20.2 Example SAS Code

20.2.1 Example SAS Code for Fisher's Exact Test and the CIs

Example SAS code for conducting Fisher's Exact Test is as follows

```
proc freq data = testData_SHP640_PBO;  
tables treatment*CS / chisq nocol nopercent;  
run;
```

Example SAS code for generating exact CI for binominal proportion is as follows:

```
proc freq data = testData_SHP640_PBO;  
tables CS / binomial (exact level='Yes') alpha=0.05;  
by treatment;  
run;
```

Example SAS code for generating the estimated difference in response rates and corresponding 95% asymptotic CI for the difference.

```
proc freq data = testData_SHP640_PBO;  
tables treatment*CS / nocol nopercent cl riskdiff alpha=0.05;  
run;
```

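### The subgroup difference intervals in SAP 13 are Wald intervals by the SAP's own code, with no small-cell rule; they under-cover in small cells and can collapse to zero width

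*SAP*

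**What the plan says.** SAP 13 plans subgroup summaries of the primary and key secondary endpoints by age stratum and by "gender, race, ethnicity, iris color of the study eye and region", with five planned regions. Each arm's rate gets a "two-sided 95% exact CI for binominal proportion". For differences between arms it adds: "Pairwise difference in response rates and corresponding two-sided 95% asymptotic CI for the difference will also be generated in mITT". It does not say which pairs are meant. No subgroup tests are planned, because "the study is not powered to detect treatment effect within subgroups".

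SAP 20.2.1 holds the only example code for a difference interval: "tables treatment*CS / nocol nopercent cl riskdiff alpha=0.05". No interval method, correction or exact option is requested. Neither document gives a minimum cell size, a pooling rule, or an alternative for cells at 0% or 100%.

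The planned mITT numbers in SAP 2.5 are "216 subjects in each of the SHP640 and placebo groups, 72 in PVP-I group", with the power calculation "assuming 61% and 45% subjects with clinical resolution, respectively". No response rate is given for PVP-I or for bacterial eradication, and no subgroup size is given anywhere.

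**The concern.** The Wald interval takes its standard error from the observed proportions. In small samples, or with rates near 0% or 100%, that standard error is often too small and can be exactly zero. The SAP guards against this for single rates by using exact intervals, but not for the difference reported with them. A subgroup row could then show two wide single-arm intervals beside a difference interval with no width at all.

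What is at stake is how the subgroup tables read. With no tests planned, a reader judges the treatment difference within a region, race or age group from the estimates and their intervals. An interval labelled 95% that covers much less overstates what the data show about that difference.

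**Working it through.** **The plan's own figure.** The documents state no coverage for these intervals. Their related figure is about 90% power for Fisher's exact test with 216 per arm at 61% versus 45%, two-sided 5%. Full enumeration gives 0.899, so the planning inputs reproduce.

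**Inputs.** From SAP 2.5: 216 SHP640, 216 placebo and 72 PVP-I in the mITT; allocation 3:1:3; rates 61% and 45%. Assumed, because the documents are silent:

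- Subgroup shares of 20%, 10%, 5% and about 4% of the mITT. These give 216 × 0.20 = 43 and 72 × 0.20 = 14; then 22 and 7; then 11 and 4. A subgroup of 21 (21/504 = 4.2%) splits 9, 3 and 9. For scale, 72 PVP-I subjects over five regions average 72/5 = 14.4.
- A higher pair of rates, 95% and 85%, because SAP 13 also applies the interval to eradication, for which no rate is stated.
- In PVP-I-sized pairs, the second rate (45% or 85%) is given to the smaller arm.

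**Formulas.** Wald: d ± 1.96 × √(p₁(1−p₁)/n₁ + p₂(1−p₂)/n₂), where d = p₁ − p₂ and both are observed rates. The comparator is the Newcombe hybrid-score interval, built from the Wilson limits (l, u) of each rate: lower limit d − √((p₁−l₁)² + (u₂−p₂)²), upper limit d + √((u₁−p₁)² + (p₂−l₂)²). Coverage is the sum of the binomial probabilities of all outcomes whose interval contains the true difference.

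**Coverage at 61% and 45%.**

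| Cell sizes | Wald | Newcombe |
|---|---|---|
| 216 vs 216 | 94.9% | 94.9% |
| 43 vs 43 | 94.9% | 93.8% |
| 22 vs 22 | 93.5% | 93.9% |
| 11 vs 11 | 91.6% | 94.8% |
| 9 vs 9 | 89.8% | 94.7% |
| 43 vs 14 | 93.0% | 95.3% |
| 22 vs 7 | 89.3% | 94.7% |
| 11 vs 4 | 84.7% | 94.9% |
| 9 vs 3 | 77.6% | 95.7% |

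**Coverage at the assumed 95% and 85%.** Wald gives 74.7% for 9 vs 9 and 34.6% for 9 vs 3. Newcombe gives 99.4% and 96.0%.

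**Zero width.** If each observed rate is 0% or 100%, both variance terms vanish. The chance of this is (p₁^n₁ + (1−p₁)^n₁) × (p₂^n₂ + (1−p₂)^n₂). For 9 vs 3:

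- At 61% and 45%: (0.61⁹ + 0.39⁹) × (0.45³ + 0.55³) = 0.0119 × 0.2575 = 0.003, or 0.3%.
- At 95% and 85%: (0.95⁹ + 0.05⁹) × (0.85³ + 0.15³) = 0.6302 × 0.6175 = 0.389, or 38.9%.

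**Example: 9/9 versus 3/3.** Wald: d = 0 and SE = 0, so the interval is (0, 0). The exact single-arm intervals are 66% to 100% (0.025^(1/9) = 0.664) and 29% to 100% (0.025^(1/3) = 0.292). For Newcombe, the Wilson lower limits are 9/(9 + 3.84) = 0.701 and 3/(3 + 3.84) = 0.439, and both upper limits are 1. The interval is −(1 − 0.701) to +(1 − 0.439), that is −30 to +56 points.

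**The case against.** The strongest objection concerns scope. SAP 13 does not name the pairs. SAP 2.6 uses the same word only for the two SHP640 versus placebo tests, and the dataset in the 20.2.1 code is named for those two arms. Including PVP-I is a fair reading of a three-arm table, but it is an inference, and the worst coverage figures depend on it. This stands. Without PVP-I, the loss at the planned rates is modest: 89.8% to 94.9% for 9 to 43 per arm.

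The small cells and the 95% and 85% rates are also assumptions. At the planned rates a zero-width interval is rare: 0.3% for 9 versus 3 and about 0.006% for 9 versus 9. This stands too.

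It can also be said that asymptotic does not by itself mean Wald, that the code is labelled as an example, and that table specifications are in a separate document (SAP 1). All true. But the code is the only method shown, and nothing in either document would prevent the result.

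Three stronger readings are tempting and unsupported:

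- **That the interval could create a false difference between regions, races or ages.** It estimates the treatment difference within one subgroup, and (0, 0) shows no difference at all.
- **That it is the only guide to uncertainty in these tables.** The exact single-arm intervals are also required and would warn a careful reader.
- **That the main results are in doubt.** They rest on Fisher's test in the full mITT, and at 216 versus 216 the Wald interval covers 94.9%.

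**Conclusion.** The point holds for small subgroup cells. Followed as written, the plan prints difference intervals labelled 95% that cover about 90% to 92% with 9 to 11 per arm for SHP640 versus placebo at the planned rates. If PVP-I pairs are included, coverage is 78% to 89% with 3 to 7 PVP-I subjects. Coverage is much lower at high response rates, where zero-width intervals also become common.

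These sizes rest on assumed subgroup shares and, for the worst figures, on assumed rates and on PVP-I being among the pairs. That the interval has zero width when each observed rate is 0% or 100% is algebra and needs no assumption.

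A reader might infer that the subgroup intervals are unreliable in general. They are not: at the planned rates, 43 versus 43 covers 94.9% and 43 versus 14 covers 93.0%. The tables are descriptive and untested, and no primary or key secondary conclusion changes.

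**What to change.** In SAP 13, specify a Newcombe or Miettinen-Nurminen interval for the subgroup differences, for example `riskdiff(cl=newcombe)`, add matching code to SAP 20.2.1, and name the pairs compared. The full-sample primary and key secondary intervals may stay as they are.

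The cost is one SAS option and a sentence or two in the SAP, settled before unmasking. SAP 16 allows SAS 9.2 or higher, so confirm that the version in use offers the option. Small-cell intervals will be wider. The subgroup tables will use a different method from the main tables unless the option is applied throughout. At the planned rates the change buys little in larger equal cells: at 43 versus 43 Newcombe covers 93.8% against 94.9% for Wald. The benefit is in the small cells.

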14. INTERIM ANALYSIS

An unmasked IA will be performed after ~50% subjects exit the trial in the mITT population, with data to be analyzed entered into the database, queried, and discrepancies resolved. The purpose of the IA will be to assess the adequacy of the initial sample size estimation by evaluating conditional power for the primary comparison of SHP640 versus placebo on clinical resolution in the treatment of subjects with bacterial conjunctivitis in the study eye at Visit 3 (Day 5). There is no intention to stop early for efficacy or futility based on the results from the IA.

The IA will be performed by an external unmasked independent statistician and/or unmasked programmers based on a prespecified interim SAP. The interim SAP will explicitly describe how the conditional power is to be calculated and the precise rules for altering the sample size depending on the potential results. The interim SAP will be finalized prior to IA. The interim statistical report including the results will be distributed only to a limited group of people who are not involved in the conduct of the trial. All sponsor, CRO, and site staff involved in the conduct of the trial must remain masked throughout the trial. Recommendation from the IA to increase the sample size may require an amendment to the study protocol. There is no inflation of type I error from this IA because the sole purpose of the planned IA is to adjust the sample size by using the conditional power approach, and the sample size will be changed only under certain conditions ([Mehta and Pocock, 2011](#)). However, for conservativeness, two sided 0.0001 alpha will be spent for the proposed IA and a two sided alpha of 0.0499 will be used for final analyses.

15. DATA MONITORING/REVIEW COMMITTEE

There is no data monitoring committee for this study.

16. COMPUTER METHODS

Statistical analyses will be performed using Version 9.2 (or higher) of SAS[®] on a suitably qualified environment.

17. CHANGES TO ANALYSES SPECIFIED IN PROTOCOL

Change from baseline BCVA has been added in Section [11.2](#), other safety variables.

18. DATA HANDLING CONVENTIONS

18.1 General Data Reporting Conventions

Continuous variables will be summarized using the following descriptive statistics: number of subjects (n), mean, median, SD, minimum, maximum unless otherwise specified. Categorical and count variables will be summarized by the number of subjects (n), frequency and the percent of subjects in each category unless otherwise specified. Percentages will be presented with one decimal point.

See TFLs4Shire for rules on the number of decimal places to present data and p-values.

18.2 Study Visits and Windows

Assessments will be assigned to visits based upon the date the assessment took place regardless of the CRF page completed. Assessments will be mapped to visits as outlined in [Table 2](#).

Should there be more than 1 assessment mapped into a given study visit, the assessment closest to the planned visit will be used for analysis (referred to as analysis visit); if equally close, choose assessment obtained on the scheduled visit or the last assessment if there is no data on the scheduled visit.

Study day will be calculated as follows:

- If the assessment date is on or after the date of first instillation:

$$\text{Study day} = \text{assessment date} - \text{first dosing date} + 1$$

- If the assessment date is before the date of first instillation:

$$\text{Study day} = \text{assessment date} - \text{first dosing date}$$

Table 2: Visit Windows (Study Day Based)

| Visit | Planned Study Day | Start Day of Window | End Day of Window |
|--------------------------------|-------------------|---------------------|-------------------|
| Visit 1 (Screening & Baseline) | 1 | Date of CRF Visit 1 | 1 |
| Visit 2 | 3 | 3 | 4 |
| Visit 3 | 5 | 5 | 6 |
| Visit 4 | 8 | 8 | 9 |
| Visit 5 | 12 | 12 | 14 |

18.3 Derived Efficacy Endpoints

Clinical resolution is defined as absence of bulbar conjunctival injection and ocular conjunctival discharge. Bulbar Conjunctival Injection will be assessed based on a 0-4 scale which uses pictures from the Validated Bulbar Redness (VBR) Scale. Ocular Conjunctival Discharge will be assessed based on a 0-3 scale. For both bulbar conjunctival injection and ocular conjunctival discharge, 0 score indicates normal or none and a higher score indicates a higher severity of the clinical sign. A 0 sum of bulbar conjunctival injection score and ocular conjunctival discharge score represents reaching clinical resolution. Any non 0 sum means not reaching clinical resolution. If either individual score is missing, clinical resolution status will be set to missing.

Bacterial eradication is defined as absence of all bacterial species present at or above pathological threshold at baseline (see Appendix 20.1 for pathological thresholds). Presence of at least one bacterial species that were at or above pathological threshold at baseline is considered not reaching bacterial eradication. If an eye has missing bacterial culture result at baseline, the eye will be assumed to be bacterial culture negative at baseline for determination of the study eye.

Global clinical score is defined as the sum of bulbar conjunctival injection score and ocular conjunctival discharge score. If either individual score is missing, global clinical score will be set to missing.

Modified clinical resolution is defined as a global clinical score of 0 or 1. All other scores are considered not reaching modified clinical resolution. If either individual score is missing, modified clinical resolution status will be set to missing.

Expanded clinical resolution is defined as a global clinical score of 0, 1, or 2 with neither bulbar conjunctival injection score nor ocular conjunctival discharge score having a score of 2. Otherwise, the subject is considered not reaching expanded clinical resolution. If either individual score is missing, expanded clinical resolution status will be set to missing.

Time to clinical resolution will be derived based upon assessments at Visits 2 (Day 3), 3 (Day 5), 4 (Day 8), and 5 (Day 12) in the study eye. Time to clinical resolution will equal to the study day corresponding to the visit when the subject first reaches clinical resolution in the study eye.

Ocular discomfort total score (in the version for adult and older children) is defined as the sum of eye pain score, the feeling that something was in your eye score and itching score. If any individual score is missing, then ocular discomfort total score will be set to missing.

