9.8.2 Primary Efficacy Endpoint

The primary efficacy endpoint is clinical resolution status (defined as absence [ie, a score of 0] of bulbar conjunctival injection and ocular conjunctival discharge) in the study eye at Visit 3 (Day 5) between SHP640 and placebo.

All efficacy analyses will be performed on the mITT population and presented by treatment groups. There is a single primary comparison for the single primary endpoint. Therefore, no adjustment of multiplicity is needed for the hypothesis testing for the primary objective.

The primary efficacy endpoint of clinical resolution in the study eye at Visit 3 (Day 5) will be compared between the SHP640 and placebo group. The comparison will be based on the proportion of subjects with clinical resolution in the study eye at Visit 3 (Day 5) using Fisher's Exact test at 2-sided 0.0499 significance level.

If subjects have missing clinical resolution status at Visit 3 (Day 5), then the last post-baseline observation will be carried forward for the determination of clinical resolution of the study eye.

The null hypothesis to be tested is that there is no difference in proportion of subjects with clinical resolution in the study eye between SHP640 ophthalmic solution and placebo with the alternative of the non-zero difference in the proportion with clinical resolution between them.

The proportion of subjects with clinical resolution will be compared with 2-sided Fisher's Exact test at 4.99% level of significance.

Sensitivity analyses will be done on the primary efficacy endpoint using additional statistical method(s) including other methods of imputation of missing data. Sensitivity analyses may be conducted in the ITT population in addition to the mITT. In addition, descriptive statistics will be generated for the primary efficacy endpoint by treatment within the overall pediatric population (ie, birth to 18 years) and within each pediatric age stratum (<6 years and 6 to <18 years) in mITT. A detailed plan for primary analysis including additional sensitivity analyses will be described in the SAP.

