10. EFFICACY ANALYSES

All efficacy analyses will be based on the mITT unless stated otherwise. Baseline for all efficacy analyses is defined as the value for the efficacy assessment at Visit 1.

All statistical tests will be 2-sided hypothesis tests performed at the 4.99% level of significance for main effects. All confidence intervals (CIs) will be 2-sided 95% CI, unless stated otherwise.

All efficacy analyses will be conducted according to the treatment assigned.

Multiplicity adjustments will be done on the primary and key secondary efficacy endpoints testing as described in Section 2.6.

Missing post-baseline efficacy assessments will be imputed using LOCF from post-baseline values and all efficacy statistical inference will be made based on analyses using LOCF, unless stated otherwise. If a subject has no post-baseline efficacy assessment then no LOCF will be done for that efficacy assessment for the subject. In other words, the subject's Visit 3 (Day 5) data will remain missing which means the subject will be excluded from the primary analysis in mITT and sensitivity analysis in ITT for that efficacy assessment.

All efficacy endpoints will be listed in the ITT Population. The listing will include a flag to indicate whether the subject is in mITT.

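### SAP 18.3 codes clinical resolution as missing even when the one recorded sign already proves failure; multiple imputation can then score that failure as resolved, and the primary LOCF analysis can drop it or, if status is carried, miscount it

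*SAP*

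**What the plan says.** SAP 18.3 scores injection 0-4 and discharge 0-3 and treats a sum of 0 as resolution. For every other sum it says: "Any non 0 sum means not reaching clinical resolution". The missing-data rule follows directly: "If either individual score is missing, clinical resolution status will be set to missing". The same convention is applied to the total score ("If either individual score is missing, global clinical score will be set to missing") and to the two relaxed endpoints ("If either individual score is missing, modified clinical resolution status will be set to missing"; "If either individual score is missing, expanded clinical resolution status will be set to missing"). None of these rules makes an exception for a recorded score that already settles the outcome.

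For the primary analysis, protocol 9.8.2 says: "If subjects have missing clinical resolution status at Visit 3 (Day 5), then the last post-baseline observation will be carried forward". SAP 10 says: "Missing post-baseline efficacy assessments will be imputed using LOCF from post-baseline values". Neither states whether the derived status or each sign score is carried. Where a subject has no post-baseline assessment to carry, SAP 10 says the Visit 3 data "will remain missing which means the subject will be excluded from the primary analysis in mITT and sensitivity analysis in ITT".

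SAP 10.3 plans two imputation checks. Modified WOCF ranks non-resolution as worse than resolution and falls back on baseline if nothing was recorded after baseline up to Visit 3. MI imputes Visit 3 GCS from treatment, age stratum, baseline GCS and Visit 2 GCS, with bounds of 0 to 7 for every subject. The example code in 20.2.2 then codes an imputed GCS of 0 as resolved.

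**The concern.** A subject whose injection is graded 2 on Day 5, with discharge not recorded, has not resolved. No value of the missing score could change that. SAP 18.3 nevertheless treats the outcome as unknown and passes the subject to imputation or exclusion.

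Three things can follow. MI, which is meant to test robustness to missing data, can produce an outcome that the recorded data exclude. The primary analysis can lose a known failure. If LOCF works on status, the primary analysis can also count that failure as a success. The primary test is a Fisher's Exact test at 0.0499 and is the gate to the key secondary test, so a single subject can matter when the result is close.

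**Working it through.** **Plan's own figure.** Inputs from SAP 2.5 and 2.6: 216 per arm, 61% versus 45%, two-sided Fisher's Exact test. Exact enumeration gives power of 89.87% at both 0.05 and 0.0499, so the stated ~90% is reproduced.

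**What one recorded score proves (scales from SAP 18.3).**
- Injection 1-4 recorded, discharge missing (0-3): possible sums are 1 to 7.
- Discharge 1-3 recorded, injection missing (0-4): possible sums are 1 to 7.
- A sum of 0 is impossible in both cases, so failure is certain. No single score proves success.
- Modified resolution is met only by the (injection, discharge) pairs (0,0), (0,1) and (1,0). Expanded resolution adds (1,1). One recorded score of 2 or more therefore rules out both.

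**One case through each method.** Visit 2: injection 0, discharge 0. Visit 3: injection 2, discharge missing.

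| Method | Visit 3 outcome under the current text |
|---|---|
| LOCF, status carried | Resolved |
| LOCF, each sign carried | Sum 2 + 0 = 2, not resolved |
| Modified WOCF, status ranked | Resolved (the only observed status was resolved) |
| MI | Resolved whenever the drawn GCS is 0 |

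If this subject had no earlier post-baseline status (status carried), or no earlier post-baseline discharge score (signs carried), Visit 3 would stay missing and SAP 10 would exclude the subject. Exclusion is thus possible under both readings. A false success in the primary test needs status to be carried.

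**Chance that MI draws 0 for a known failure.** Model: normal draw around the predicted GCS, rounded and kept within 0-7. The residual SD of 1 to 1.5 is an assumption. The ranges cover both SDs and bounding before or after rounding.

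| Predicted GCS | Chance per imputation |
|---|---|
| 1 | 16-26% |
| 2 | 5-12% |
| 3 | 0.5-4% |

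**Expected number of subjects.** The documents give no rate of partly missing assessments. Assume a fraction f = 0.5-2% of an arm has one sign above 0 and the other missing on Day 5.
- LOCF with status carried, and an assumed g = 10-30% of these subjects resolved at Visit 2: 216 × f × g runs from 216 × 0.005 × 0.10 = 0.11 to 216 × 0.02 × 0.30 = 1.30 per arm. One subject is 1/216 = 0.46 percentage points.
- MI: 216 × 0.005 × 0.005 = 0.005 to 216 × 0.02 × 0.26 = 1.1 subject-equivalents per arm.

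**Effect on the test.** One extra success in each arm leaves power at 89.88%. Near the border (constructed example, placebo 97/216):

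| SHP640 | Two-sided Fisher p |
|---|---|
| 118/216 | 0.0542 |
| 119/216 (one failure scored as success) | 0.0432 |
| 118/215 (one known failure dropped) | 0.0432 |

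One miscount in each arm cancels: 119/216 versus 98/216 gives 0.0542 again.

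**The case against.** A reader might infer that the primary analysis will count recorded failures as successes. The documents do not support that as a general statement. The protocol triggers LOCF on a missing status, but it carries an observation in order to determine resolution, which also fits carrying sign scores. SAP 10 speaks of assessments, and the schedule lists injection and discharge as separate evaluations. Only the WOCF ranking clearly works on status, and WOCF is a sensitivity analysis. This part of the objection stands: what is carried is unspecified. It does not follow that carrying signs removes the problem, because a missing sign with no earlier post-baseline score still leads to exclusion.

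It is also fair to say that requiring both components is an ordinary convention for a sum, and that the definition and the missing-data rule are not in formal contradiction. For GCS the convention is sound. For a binary endpoint that one component can decide, it throws away a known result.

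Finally, the pattern should be rare. Both signs are scheduled at every visit, omissions are queried, and uncompleted procedures are protocol deviations. A false success by LOCF also needs a subject who was clear at the last earlier post-baseline assessment and had signs again by Day 5. The rule is the same in both masked arms, so there is no reason to expect it to favour SHP640. All of this stands and limits the size of the point. It does not answer the MI problem, which exists however LOCF is read. Modified WOCF does count as failures those with no post-baseline assessment up to Visit 3, since an eligible eye scores at least 1 on both signs at baseline.

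**Conclusion.** The point holds as a defect in the derivation rule. SAP 18.3 declares a determined outcome missing, and nothing elsewhere in the documents restores it. For MI the consequence follows without further conditions: a known Day 5 failure can be scored resolved. For the primary analysis, exclusion of a known failure is possible under either reading of LOCF. A false success requires status to be carried and the last earlier post-baseline status to have been resolved. For modified WOCF, the corresponding condition is that every observed post-baseline status up to Day 5 was resolved.

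The size is small: about one subject per arm or fewer, on frequencies and a residual SD that are assumed and not taken from the documents. Sample size and planned power are unaffected. The result would change only if the primary test fell close to 0.0499. The relaxed endpoints share the flaw but are descriptive only. The rule should be corrected, since the correction is nearly free and avoids having to settle such cases after they have been seen.

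**What to change.** - **SAP 18.3, clinical resolution:** *If any observed sign score is above 0, clinical resolution status is not resolved even if the other score is missing; status is missing only when no observed score is above 0.*
- **SAP 18.3, modified and expanded resolution:** *If any observed sign score is 2 or more, status is not resolved even if the other score is missing.* GCS itself stays missing, because the sum is unknown.
- **SAP 10.3 and 20.2.2:** after MI, keep status as not resolved for any subject with an observed Visit 3 sign above 0, whatever GCS was drawn.
- **SAP 10:** state whether LOCF and WOCF carry the status or each sign. This still matters when the observed sign is 0. With Visit 2 injection 1 and discharge 0, then Day 5 injection 0 and discharge missing, carrying signs gives resolved and carrying status gives not resolved.

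The cost is two sentences in SAP 18.3, one in SAP 10 and one line in the MI code. Data collection, the primary test, the sample size and the table list do not change.
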